13.9.18. Impact on Creatinine

Medical concept of worsening renal function/renal failure in the context of impact on creatinine. Only narrow terms from SMQ 'Acute renal failure' plus all PTs from HLT 'Renal failure and impairment', under SOC 'Renal and urinary disorders'. Numerous duplicated preferred terms e.g. renal failure

SMQ: 'Acute renal failure' SMQ Code: 20000003 Category: A Scope: Narrow	
Preferred Term	PT Code
Acute kidney injury	10069339
Acute phosphate nephropathy	10069688
Anuria	10002847
Azotaemia	10003885
Continuous haemodiafiltration	10066338
Dialysis	10061105
Foetal renal impairment	10078987
Haemodialysis	10018875
Haemofiltration	10053090
Neonatal anuria	10049778
Nephropathy toxic	10029155
Oliguria	10030302
Peritoneal dialysis	10034660
Prerenal failure	10072370
Renal failure	10038435
Renal failure neonatal	10038447
Renal impairment	10062237
Renal impairment neonatal	10049776
Subacute kidney injury	10081980

Renal Failure and Impairment HLT, HLT Code 10038443	
Preferred Term	PT Code
Acute Kidney injury	10069339
Anuria	10002847
Atypical haemolytic uraemic syndrome	10079840
Cardiorenal syndrome	10068230
Chronic kidney disease	10064848
Crush syndrome	10050702
Diabetic end stage renal disease	10012660
End stage renal disease	10077512
Foetal renal impairment	10078987
Haemolytic uraemic syndrome	10018932
Hepatorenal failure	10019845
Hepatorenal syndrome	10019846
Nail-patella syndrome	10063431
Neonatal anuria	10049778
Oliguria	10030302
Pancreatorenal syndrome	10056277
Postoperative renal failure	10056675
Postrenal failure	10059345
Prerenal failure	10072370
Propofol infusion syndrome	10063181
Renal failure	10038435
Renal failure neonatal	10038447
Renal impairment	10062237
Renal impairment neonatal	10049776
Renal injury	10061481
Scleroderma renal crisis	10062553
Traumatic anuria	10044501

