10.5.1. Definition of Adverse Events

Adverse Event Definition:

- An AE is any untoward medical occurrence in a patient or clinical investigation participant, temporally associated with the use of a medicinal product, whether or not considered related to the medicinal product.
- NOTE: An AE can therefore be any unfavorable and unintended sign (including an abnormal laboratory finding), symptom, or disease (new or exacerbated) temporally associated with the use of a medicinal product.

Events meeting AE definition include:

- Any abnormal laboratory test results (hematology, clinical chemistry, or urinalysis) or other safety assessments (e.g., ECGs, radiological scans, vital signs measurements), including those that worsen from baseline, and felt to be clinically significant in the medical and scientific judgement of the investigator.
- Exacerbation of a chronic or intermittent pre-existing condition including either an increase in frequency and/or intensity of the condition.
- New conditions detected or diagnosed after study treatment administration even though it may have been present prior to the start of the study.
- Signs, symptoms, or the clinical sequelae of a suspected interaction.
- Signs, symptoms, or the clinical sequelae of a suspected overdose of either study treatment or a concomitant medication (overdose per se will not be reported as an AE/SAE unless this is an intentional overdose taken with possible suicidal/selfharming intent. This should be reported regardless of sequelae).
- "Lack of efficacy" or "failure of expected pharmacological action" per se will not be reported as an AE or SAE. However, the signs and symptoms and/or clinical sequelae resulting from lack of efficacy will be reported if they fulfil the definition of an AE or SAE.

Events **NOT** meeting definition of an AE include:

- Any clinically significant abnormal laboratory findings or other abnormal safety assessments which are associated with the underlying disease, unless judged by the Investigator to be more severe than expected for the participant's condition.
- The disease/disorder being studied or expected progression, signs, or symptoms of the disease/disorder being studied, unless more severe than expected for the participant's condition.
- Medical or surgical procedure (e.g., endoscopy, appendectomy): the condition that leads to the procedure is an AE.

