10.6.5.6. Decline in Renal Function

Participants who experience an increase in serum creatinine from Baseline of 45 micromoles/liter (μ Mol/L) (or 0.5 milligrams/deciliter [mg/dL]) should return for a confirmatory assessment within 2 to 4 weeks. A urinalysis and urine albumin/creatinine and urine total protein/albumin ratios should also be done at this confirmatory visit. If the creatinine increase is confirmed, the Investigator should contact the study medical monitor to discuss additional follow-up and medical management.

Participants who have a decline in the estimated GFR (using the CKD-EPI method) of >50% from Baseline must return for a confirmatory assessment as soon as possible [Levey, 2009]. A urinalysis and urine albumin/creatinine and urine protein/creatinine ratios should also be done at this confirmatory visit. If the estimated GFR has declined by >50% (confirmed), then study drug should be withheld and the Investigator should contact the study medical monitor to discuss the rationale for restarting study drugs (if appropriate). Consideration for confounding factors (e.g., background therapy, other medications, dehydration, concurrent conditions) should be taken into account, and a nephrology consult may be obtained.

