13.9.15. Weight Gain

Medical concept of weight gain. Selected PTs from HLT 'General nutritional disorders NEC', under SOC 'Metabolism and nutrition disorders', and HLT 'Physical examination procedures and organ system status', under SOC 'Investigations' and HLT 'General signs and symptoms NEC', under SOC 'General disorders and administration site conditions'.

PTs (Select) from HLT General nutritional disorders NEC, HLT code 10018067	
Preferred Term	PT Code
Abdominal fat apron	10077983
Overweight	10033307
Abnormal weight gain	10000188
Central obesity	10065941
Obesity	10029883
Abdominal fat apron	10077983
Overweight	10033307
Abnormal weight gain	10000188
Central obesity	10065941
Obesity	10029883
PTs (Select) from HLT Physical examination procedures and organ system status, HLT Code 10071941	
Preferred Term	PT Code
Weight abnormal	10056814
Weight increased	10047899
Waist circumference increased	10064863
Body mass index abnormal	10074506
Body mass index increased	10005897
PTs (Select) from HLT General signs and symptoms NEC, HLT Code 10018072	
Preferred Term	PT Code
Fat tissue increased	10016251
Sarcopenic obesity	10083992

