13.9.16. Rhabdomyolysis

Medical concept of rhabdomyolysis. Only narrow terms only for SMQ 'Rhabdomyolysis/myopathy' plus 2 additional preferred terms selected from HGLT 'muscle disorders' under SOC 'Musculoskeletal and connective tissue disorders'.

SMQ: 'Rhabdomyolysis/myopathy'	
SMQ Code: 20000002	
Category: A	
Scope: Narrow	
Preferred Term	PT Code
Muscle necrosis	10028320
Myoglobin blood increased	10028625
Myoglobin blood present	10059888
Myoglobin urine present	10028631
Myoglobinaemia	10058735
Myoglobinuria	10028629
Myopathy	10028641
Myopathy toxic	10028648
Necrotising myositis	10074769
Rhabdomyolysis	10039020
Thyrotoxic myopathy	10081524
PTs (Select) from HGLT muscle disorders, HLGT Code 10028302	
Preferred Term	PT Code
Myalgia	10028411
Myositis	10028653

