3.62.	Safety	201584/primary_07/T3.140	Summary of Hypersensitivity Reactions (HSR) Adverse Events of Special Interest by System Organ Class and Preferred Term (Number of Subjects and Occurrences)		M12, EOS
3.63.	Safety	201584/primary_07/T3.143	Summary of Rash Adverse Events of Special Interest by System Organ Class and Preferred Term (Number of Subjects and Occurrences)		M12, EOS

CONFIDENTIAL

213199

Safety: Tables					
3.64.	Safety	201584/primary_07/T3.149	Summary of Bipolar Disorder Adverse Events of Special Interest by System Organ Class and Preferred Term (Number of Subjects and Occurrences)		M12, EOS
3.65.	Safety	201584/primary_07/T3.152	Summary of Psychosis Adverse Events of Special Interest by System Organ Class and Preferred Term (Number of Subjects and Occurrences)		M12, EOS
3.66.	Safety	201584/primary_07/T3.155	Summary of Mood Disorders Adverse Events of Special Interest by System Organ Class and Preferred Term (Number of Subjects and Occurrences)		M12, EOS
3.67.	Safety	201584/primary_07/T3.158	Summary of Sleep Disorders Adverse Events of Special Interest by System Organ Class and Preferred Term (Number of Subjects and Occurrences)		M12, EOS
3.68.	Safety	201584/primary_07/T3.161	Summary of Hyperglycaemia Adverse Events of Special Interest by System Organ Class and Preferred Term (Number of Subjects and Occurrences)		M12, EOS
3.69.	Safety	201584/primary_07/T3.161	Summary of Weight Gain Adverse Events of Special Interest by System Organ Class and Preferred Term (Number of Subjects and Occurrences)		M12, EOS
3.70.	Safety	201584/primary_07/T3.164	Summary of Rhabdomyolysis Adverse Events of Special Interest by System Organ Class and Preferred Term (Number of Subjects and Occurrences)		M12, EOS
3.71.	Safety	201584/primary_07/T3.167	Summary of Pancreatitis Adverse Events of Special Interest by System Organ Class and Preferred Term (Number of Subjects and Occurrences)		M12, EOS
3.72.	Safety	201584/primary_07/T3.170	Summary of Impact on Creatinine Adverse Events of Special Interest by System Organ Class and Preferred Term (Number of Subjects and Occurrences)		M12, EOS

Safety: Tables					
3.73.	Safety	201584/primary_07/T3.173	Summary of Safety in Pregnancy Adverse Events of Special Interest by System Organ Class and Preferred Term (Number of Subjects and Occurrences)		M12, EOS
3.74.	Safety	207966/primary_15/T3.109	Summary of Characteristics of Adverse Events of Special Interest		M12, EOS

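### The 'Impact on Creatinine' AESI lists no creatinine, creatinine-clearance or GFR term, so an isolated rise reported as an AE would be missing from the table of that name

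*SAP*

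**What the plan says.** SAP 13.9.18 (Appendix 9) is headed 'Impact on Creatinine'. It describes the concept as "Medical concept of worsening renal function/renal failure in the context of impact on creatinine" and gives its sources: "Only narrow terms from SMQ 'Acute renal failure' plus all PTs from HLT 'Renal failure and impairment', under SOC 'Renal and urinary disorders". It adds a remark on overlap between the two: "Numerous duplicated preferred terms e.g. renal failure". Both sets of preferred terms are printed with their codes.

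The list feeds Table 3.72 in SAP 13.12.7, planned for Month 12 and end of study: "Summary of Impact on Creatinine Adverse Events of Special Interest by System Organ Class and Preferred Term". Table 3.74 summarises the characteristics of the AESIs as a group.

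SAP 8.3 says that the terms used will follow the safety review team's agreements at the time of reporting, and presents Appendix 9 as the grouping planned at present.

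On the protocol side, section 10.5.1 counts this among events that meet the AE definition: "Any abnormal laboratory test results (hematology, clinical chemistry, or urinalysis", if the investigator judges the result clinically significant. Section 10.6.5.6 opens with "Participants who experience an increase in serum creatinine from Baseline of 45 micromoles/liter" (0.5 mg/dL) and calls for a confirmatory assessment. It does the same for a fall in estimated GFR of more than 50%.

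**The concern.** The title of the AESI and its table names a laboratory measurement, but the terms behind them are renal diagnoses, urine-output terms and dialysis procedures. The protocol foresees creatinine rises and GFR falls, follows them up, and lets them be reported as AEs. If one is reported as a laboratory finding and coded to a term of that kind, the table named for it has no place to count it.

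What is at stake is how a safety table is read. A zero or low count in Table 3.72 would naturally be taken to mean that few or no creatinine AEs occurred, when the table was never able to show them.

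**Working it through.** The plan gives no figure to reproduce here, so the check is a count and a term search of the printed list, followed by a comparison with the other AESIs in the same appendix.

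**Count (SAP 13.9.18)**
- Terms printed from the narrow 'Acute renal failure' SMQ: 19.
- Terms printed from the HLT 'Renal failure and impairment': 27.
- Codes in both: 10 (acute kidney injury, anuria, foetal renal impairment, neonatal anuria, oliguria, prerenal failure, renal failure, renal failure neonatal, renal impairment, renal impairment neonatal).
- Unique terms: 19 + 27 − 10 = 36.

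**Search.** Terms among the 36 that contain creatinine, clearance, GFR, glomerular or filtration rate: 0 of 36. The nearest to a laboratory finding is azotaemia, which does not name creatinine. The list does include nail-patella syndrome, propofol infusion syndrome and crush syndrome.

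**Is there a general rule against measurement terms?** No. Elsewhere in Appendix 9:
- 13.9.2, hyperglycaemia: includes blood glucose increased and glycosylated haemoglobin increased.
- 13.9.5, QT prolongation: includes the ECG finding of a prolonged QT.
- 13.9.15, weight gain: adds hand-picked terms, weight increased among them, from "HLT 'Physical examination procedures and organ system status', under SOC 'Investigations".
- 13.9.16, rhabdomyolysis: includes "Myoglobin blood increased".

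The creatinine AESI is named after a measurement, draws on no Investigations source, and gives no reason for leaving one out.

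**Where such an AE would and would not appear**
- Not in Table 3.72, and not in Table 3.74 if that is built from the same list.
- Still in Tables 3.10 and 3.11 (all AEs), 3.18 and 3.19 (drug-related AEs), and 3.32 (AEs leading to discontinuation, by system organ class and preferred term), all planned at Month 12 and end of study.
- Still in Listing 14 (all AEs; headline and Month 12 only) and, if it led to discontinuation, in Listing 23.
- The creatinine values themselves are still in Table 3.40 (change from baseline) and Table 3.42 (grade shifts). These report laboratory results, not what investigators recorded as AEs.

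**The case against.** The case on the other side is substantial, and much of it stands.

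- **The list is provisional.** SAP 8.3 lets the safety review team revise the terms before reporting. That is correct, and it means the gap can be closed without touching the design. But it permits the correction without making it; the printed list is the present plan.
- **The events are not lost.** A reader might infer that drug-related creatinine AEs, or ones that led to discontinuation, could go unseen in the report. The documents do not support that: the tables and listings set out above would carry them. The effect is limited to Table 3.72 and possibly Table 3.74.
- **Some creatinine rises will be captured.** Protocol 10.5.4 tells investigators to record a diagnosis, where one is made, in place of its signs. A rise recorded as renal impairment or acute kidney injury is on the list. A confirmed GFR fall above 50% might well be recorded that way. What is missed is the abnormality reported on its own.
- **The concept may be meant as renal failure.** The hepatic AESI has no ALT or AST term and the pancreatitis AESI no lipase term, although the protocol monitors both. So leaving an isolated laboratory term out can be a deliberate choice in favour of specificity. But those two AESIs are not named after the laboratory test; this one is. If renal failure is the intended concept, it is the title that is wrong.

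A reader might also see the same gap in the rhabdomyolysis AESI, which has no creatine phosphokinase term although protocol 10.6.5.4 deals with that elevation. That does not hold. The AESI and its table are named and defined as rhabdomyolysis, so title and content agree, and 10.6.5.4 itself treats such rises as possibly transient or due to exercise.

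**Conclusion.** The point holds as a mismatch between a named safety table and its term list: 0 of 36 unique terms would pick up an AE coded to creatinine, creatinine clearance or GFR. How many AEs this affects cannot be stated, because the documents give no expected rate.

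Two assumptions carry the conclusion. First, an isolated creatinine or GFR abnormality reported as an AE would code to a term of that kind. The documents do not show the coding; this is inferred from the way other laboratory findings appear as preferred terms in the same appendix. Second, for Table 3.74 only, that summary uses the 13.9.18 list.

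The endpoints, the comparison between implementation arms and the efficacy results are unaffected. No clinical management rule is in question: the protocol's renal section is cited only to show that these events are anticipated. The matter is worth settling before reporting because it changes what a titled safety table says and is cheap to correct.

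**What to change.** Add the creatinine, creatinine-clearance and GFR preferred terms to SAP 13.9.18. The documents do not print them, so their names and codes should be confirmed in the MedDRA version in use (13.9 gives 23.1 for the Month 12 analysis) and agreed with the safety review team under section 8.3. In Table 3.72, show them as a row separate from clinical renal failure, so that laboratory findings do not blur the count of diagnoses. State whether Table 3.74 uses the same list.

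If the team intends renal failure only, rename the AESI and Table 3.72 'Renal failure/impairment' and leave the terms as they are.

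The cost is a SAP wording change and, for the first option, a few extra codes. The AESI count may come out slightly higher. No data collection changes.

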13.9.19. Safety During Pregnancy

Use AE terms co-reported in pregnancy exposures to CAB.

13.10. Appendix 10: Identification of COVID-19 Adverse Events

COVID-19 adverse events are identified based on MedDRA coded values and/or AE referenced in the COVID-19 Coronavirus Infection assessment. The Lowest Level Terms (LLTs) and codes, Preferred Terms (PTs), High Level Terms (HLTs), High Level Group Terms (HLGTs), and System Organ Classes (SOCs), below are from MedDRA 23.0. In case there is a change to the version of MedDRA at time of reporting, the coded values based on the MedDRA version at the time of reporting will be used. The additional events may also be added based on the blinded review of AE data collected on study prior to the database freeze.

SOC: Infections and infestations

LLT code	LLT	PT	HLT	HLGT
10084459	Asymptomatic COVID-19	Asymptomatic COVID-19	Coronaviruses infections	Viral infectious disorders
10084467	Asymptomatic SARS-CoV-2 infection	Asymptomatic COVID-19	Coronaviruses infections	Viral infectious disorders
10053983	Corona virus infection	Coronavirus infection	Coronaviruses infections	Viral infectious disorders
10051905	Coronavirus infection	Coronavirus infection	Coronaviruses infections	Viral infectious disorders
10084382	Coronavirus disease 2019	COVID-19	Coronaviruses infections	Viral infectious disorders
10070255	Coronavirus test positive	Coronavirus test positive	Virus identification and serology	Microbiology and serology investigations
10084460	COVID-19 treatment	COVID-19 treatment	Antiinfective therapies	Therapeutic procedures and supportive care NEC
10084639	SARS-CoV-2 sepsis	SARS-CoV-2 sepsis	Coronaviruses infections	Viral infectious disorders
10084271	SARS-CoV-2 test positive	SARS-CoV-2 test positive	Virus identification and serology	Microbiology and serology investigations

LLT code	LLT	PT	HLT	HLGT
10084640	SARS CoV-2 viraemia	SARS CoV-2 viraemia	Coronaviruses infections	Viral infectious disorders
10084268	COVID-19	COVID-19	Coronaviruses infections	Viral infectious disorders
10084401	COVID-19 respiratory infection	COVID-19	Coronaviruses infections	Viral infectious disorders
10084270	SARS-CoV-2 acute respiratory disease	COVID-19	Coronaviruses infections	Viral infectious disorders
10084272	SARS-CoV-2 infection	COVID-19	Coronaviruses infections	Viral infectious disorders
10084381	Coronavirus pneumonia	COVID-19 pneumonia	Coronaviruses infections	Viral infectious disorders
10084380	COVID-19 pneumonia	COVID-19 pneumonia	Coronaviruses infections	Viral infectious disorders
10084383	Novel COVID-19-infected pneumonia	COVID-19 pneumonia	Coronaviruses infections	Viral infectious disorders
10084451	Suspected COVID-19	Suspected COVID-19	Coronaviruses infections	Viral infectious disorders
10084452	Suspected SARS-CoV-2 infection	Suspected COVID-19	Coronaviruses infections	Viral infectious disorders
10084461	SARS-CoV-2 carrier	SARS-CoV-2 carrier	Infectious disorders carrier	Ancillary infectious topics

13.11. Appendix 11: Abbreviations & Trade Marks

13.11.1. Abbreviations

Abbreviation	Description
ADaM	Analysis Data Model
AE	Adverse Event
AIC	Akaike's Information Criteria
A&R	Analysis and Reporting
CDISC	Clinical Data Interchange Standards Consortium
CI	Confidence Interval
CPMS	Clinical Pharmacology Modelling & Simulation
CS	Clinical Statistics
CSR	Clinical Study Report
CTR	Clinical Trial Register
CV _b / CV _w	Coefficient of Variation (Between) / Coefficient of Variation (Within)
DBF	Database Freeze
DBR	Database Release
DOB	Date of Birth
DP	Decimal Places
eCRF	Electronic Case Record Form
EMA	European Medicines Agency
FDA	Food and Drug Administration
FDAAA	Food and Drug Administration Clinical Results Disclosure Requirements
GSK	GlaxoSmithKline
IA	Interim Analysis
ICH	International Conference on Harmonization
IDMC	Independent Data Monitoring Committee
IDSL	Integrated Data Standards Library (GSK Standards Library)
IMMS	International Modules Management System
IP	Investigational Product
ITT	Intent-To-Treat
MMRM	Mixed Model Repeated Measures
PBMC	Peripheral Blood Mononuclear Cells
PCI	Potential Clinical Importance
PD	Pharmacodynamic
PDMP	Protocol Deviation Management Plan
PK	Pharmacokinetic
PP	Per Protocol
PopPK	Population PK
QC	Quality Control
QTcF	Frederica's QT Interval Corrected for Heart Rate
QTcB	Bazett's QT Interval Corrected for Heart Rate
RAP	Reporting & Analysis Plan
RAMOS	Randomization & Medication Ordering System
SAC	Statistical Analysis Complete

Abbreviation	Description
SDSP	Study Data Standardization Plan
SDTM	Study Data Tabulation Model
SOP	Standard Operation Procedure
TA	Therapeutic Area
TFL	Tables, Figures & Listings

13.11.2. Trademarks

Trademarks of the GlaxoSmithKline Group of Companies
Cabotegravir

Trademarks not owned by the GlaxoSmithKline Group of Companies
Rilpivirine
SAS

13.12. Appendix 12: List of Data Displays

All data displays will use the term “subject” rather than “participant” in accordance with CDSIC and GSK Statistical Display Standards.

Where applicable, all summary displays will present data across both the Intervention and Extension phases unless explicitly stated otherwise in the display title.

At EOS, the RAPIDO Data Viewer will be produced to allow for the clinical team to review ADaM data directly related to adverse events, exposure, HIV-1 RNA, and labs. This will take the place of some, previously standard generic listings from these categories. Listings including results of pregnancy details will only be included if a pregnancy occurs.

13.12.1. Data Display Numbering

The following numbering will be applied for RAP generated displays:

Section	Tables	Figures
Study Population	1.1 to 1.27	
Efficacy	2.1 to 2.16	2.1 to 2.4
Safety	3.1 to 3.75	3.1 to 3.4
Other	4.1 to 4.4	
Section	Listings	
ICH Listings	1 to 24	
Other Listings	25 to 57	

13.12.2. Mock Example Shell Referencing

Nonstandard specifications will be referenced as indicated below (where a study specific mock shell is available) or the location of a similar display produced for a different study in the HARP reporting environment will be provided as reference. If required example mock-up displays provided in [Appendix 13: Example Mock Shells for Data Displays](#).

Section	Figure	Table	Listing
Study Population	POP_Fn	POP_Tn	POP_Ln
Efficacy	EFF_Fn	EFF_Tn	EFF_Ln
Safety	SAF_Fn	SAF_Tn	SAF_Ln
Other	OTR_Tn	OTR_Fn	OTR_Ln

